End of Study Visit will be conducted at Week 65. For subjects that prematurely discontinue study drug for any reason, the EOT visit should be completed within 14 days of withdrawal, Safety follow-up visit should be completed at 8 weeks and PK/ADA follow-up visit should be completed 14 weeks after the last dose of study drug, respectively, where possible. Subjects should continue to complete study assessments as outlined in the SoA (Section 1.3 of 22104 protocol) where possible, with the exception of study drug administration and anti-drug antibody sample and PK sample collection.

The final analysis of primary and secondary endpoints will be conducted after the last subject has had the opportunity to complete Week 16 assessments or prematurely discontinues the study drug and/or study.

Before database lock, an error was discovered in dosing for subjects who were randomized to receive izokibep 160 mg every 2 weeks (Q2W) from Day 1/Week 0 to Week 50, with matching placebo Q2W and subjects who were randomized to receive izokibep 80 mg every 4 weeks (Q4W) from Day 1/Week 0 to Week 48, with matching placebo QW until Week 51. Subjects were assigned study drug in groups of four visits at a time. The order in which the subject was instructed to receive the drug was incorrect. Therefore, each subject was assigned the correct amount of study drug over each 4-week period, but possibly in the wrong sequence, resulting in subjects who were randomized to receive active drug Q2W receiving active drug on two or more consecutive weeks and/or placebo at two or more consecutive weeks. Subjects who were randomized to receive active drug Q4W similarly received active drug at two or more consecutive weeks and/or placebo at four or more consecutive weeks. As a result of this error, the following changes were made to the analysis plan:

- Testing of all primary and secondary endpoints, comparing izokibep Q2W versus placebo, will only be done after testing of all primary and secondary endpoints, comparing izokibep QW versus placebo, in the alpha-controlled testing sequence.

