#### 5.1.4. Visit Windows

All data will be analyzed using the nominal study visit as defined in the SoA in the protocol and eCRF.

In the event that a subject discontinues the study early, the subject will have an early termination visit which includes efficacy assessments. If the early termination visit or an unscheduled visit occurs in a timeframe that corresponds to a scheduled efficacy assessment (week 2, 4, 12, 16, 20, 24, 32, 36, 40 or 52), and if the subject does not have an actual visit at or after the corresponding scheduled efficacy assessment, the following day ranges will be used to map the early termination/unscheduled visit to a scheduled efficacy assessment for use in all efficacy summaries at that timepoint. Similarly, if an unscheduled efficacy assessment occurs during a timeframe that corresponds to a scheduled efficacy assessment, it will be windowed accordingly, provided the subject does not have an actual visit at the same nominal time.

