## 6. Statistical Methods

### 6.1. General Principles

All data processing, summarization, and analyses will be performed using [REDACTED] SAS Environment/Version 9.4 (or later) of the SAS® statistical software package.

The default summary statistics for quantitative variables will be the number of observations (n), mean, standard deviation (SD), median, minimum (min), and maximum (max), for those subjects with data.

For qualitative variables, the number (n) and percentage (%) of subjects with non-missing data per category will be the default summary presentation, and where appropriate and present, the number of missing values as a “Missing” category. Number of subjects in the analysis population will be used as denominator for percentages calculation, unless stated otherwise in TFLs mock shell(s).

The treatment group labels and presentation order are given below:

Full treatment group label:	Short treatment group label:	Treatment group ordering:
Placebo QW Week 0 to Week 15; Izokibep 160 mg QW Week 16 to Week 51	Placebo QW - Izokibep QW	1
Izokibep 80 mg Q4W Week 0 to Week 48; Placebo QW Week 1 to Week 51 for the Weeks in Between Izokibep Doses	Izokibep SC 80 mg Q4W	2
Izokibep 160 mg Q2W Week 0 to Week 50; Placebo Q2W Week 1 to Week 51	Izokibep SC 160 mg Q2W	3
Izokibep 160 mg QW Week 0 to Week 51	Izokibep SC 160 mg QW	4

All statistical comparisons of the primary and secondary endpoints will be made using two-sided tests at the  $\alpha = 0.05$  significance level (with decisions also requiring consideration of multiplicity as defined below) unless specifically stated otherwise. All null hypotheses will be of no treatment difference. All alternative hypotheses will be two-sided.

All laboratory test results will be received from the central/local laboratories, and the results will be provided in either standard internal (SI) or conventional units, or both. For the TFLs, the results will be summarized or presented in International System of Units (SI) units. Refer to Appendix of the TFLs mock shells for the SI unit corresponding to each laboratory test. Refer to Appendix of the TFL shells for the precision level in which each laboratory test is reported by the central laboratories.

Specifications for table, figures and data listing formats can be found in the TFL shells specifications for this study. Please refer to “2. General Format Guidelines” section within TFL shells for more details on presentation of results.

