## 6.5. Measurements of Study Drug Compliance

Study Drug compliance is defined as the number of doses that were actually taken relative to the number of doses that should have been taken as per the protocol for the planned duration of treatment exposure. A partial dose in eCRF will be treated as a half dose. Study drug compliance will be summarized for period 1 and period 2 separately.

In general, the percentage of overall compliance, assessed by dose count, will be calculated as follows:

For Period 1

$$\text{Compliance (\%)} = \frac{(\text{Total doses administered from Week 0 up to before Week 16})}{\text{Total doses expected to be administered from Week 0 to before Week 16}} \times 100\%$$

For Period 2

$$\text{Compliance (\%)} = \frac{(\text{Total doses administered from Week 16 to EOT})}{\text{Total doses expected to be administered from Week 16 to EOT}} \times 100\%$$

For group 3 and group 4, matching placebo will be counted in the calculation of total doses administered and total doses expected. The total number of doses expected to be administered during Period 1 is therefore 16 for all groups. The total number of doses expected to be administered during Period 2 will be different after accounting for study drug withdrawal for those who meet criteria at or after week 24.

The calculated percentage compliance will be categorized as:

- < 80% compliance
- $\geq 80\%$

Compliance will be summarized for the Safety Analysis Set by treatment group as follows:

- Number of doses will be presented by default summary statistics. This will include both number of doses of izokibep and number of doses of placebo.
- Percent compliance will be presented by default summary statistics.
- Number and percentage of subjects within each of the compliance categories will be presented. Treatment compliance will be listed for the Safety Analysis Set. Missing data will not be imputed and only original data for those fields (for example, date fields) will be presented in the listing together with derived variables such as the calculated compliance (%) and exposure duration.

Treatment compliance will be listed for the Safety Analysis Set. Missing data will not be imputed and only original data for those fields (for example, date fields) will be presented in the listing together with derived variables such as the calculated compliance (%) and exposure duration.

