### 6.6.1. Primary Efficacy Analysis

The primary efficacy variable is defined as ACR50, the proportion of subjects achieving 50% improvement in ACR core set measurements.

The statistical null and alternative hypotheses to be used to assess the primary objective are:

$$H_0: \pi_{ABY} - \pi_{PBO} = 0$$

$$H_A: \pi_{ABY} - \pi_{PBO} \neq 0$$

where  $\pi_{ABY}$  and  $\pi_{PBO}$  are the proportion of subjects achieving ACR50 at Week 16 among subjects randomly assigned to receive izokibep and placebo, respectively. One set of hypotheses will be tested for each dose frequency of izokibep (QW and Q2W).

The treatment strategy approach for the estimand will be used in general, so subjects will be included using observed data at Week 16 regardless of treatment discontinuation, concomitant medication, protocol deviations, or other actions. Subjects with missing ACR50 assessments at Week 16 will be imputed as non-responders (non-response imputation or NRI).

Three components of the primary endpoint (subject's assessment of pain, subject's global assessment of disease activity, and investigator's global assessment of disease activity) were assessed using a visual analog scale (VAS), consisting of a horizontal line, 100 mm in length, with anchor statements at either end. The subject or investigator was asked to place a single vertical line through the VAS at the point that best corresponds to assessment. At some sites, and for some subjects, the VAS was not administered as intended. If a line was not 100 mm in length, the score used for analysis was calculated as  $100 \times (\text{distance from left to mark}) / (\text{total length of horizontal line})$ . If the subject was requested to write a number or was verbally asked for a number, that value will be used for analysis. Such protocol deviations will be noted in listings, and sensitivity analyses will be reported to assess the impact of such deviations. A spreadsheet will be created, after database lock and before unblinding, to note which subjects answered questions using a different length line, or by writing or verbally responding with a number. This spreadsheet will be signed and dated, and entered into the study files, before database lock to verify the protocol deviations and sensitivity analyses defined below.

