If there are no subjects who meet one of the protocol deviation criteria (data collected on a 0 to 10 scale, data collected verbally, or data collected using a line not 100 mm) then the corresponding subgroup analysis above will be omitted.

**Q2W and Q4W Supplemental Analyses:** A supplemental analysis is planned for subjects who were randomized to receive izokibep Q2W or izokibep Q4W. The analysis of subjects randomized to receive izokibep Q2W will group subjects according to the longest number of consecutive doses of izokibep or placebo that were received within the first 16 weeks of treatment of Period 1:

- Did not receive consecutive doses of izokibep or placebo
- Received consecutive doses, but no more than two consecutive doses of either izokibep or placebo
- Received at least three consecutive doses of izokibep or placebo, but not four consecutive doses.
- Received four or more consecutive doses of izokibep or placebo.

Because the number of subjects in the first group who did not receive consecutive doses of izokibep or placebo is expected to be small, the first two groups will be combined. The primary analysis will be run in each of the resulting three subsets of subjects, comparing each subset of subjects to the entire group of placebo subjects. Subjects will be classified according to doses actually received (not assigned), and included only if the subjects receive at least 8 total doses (izokibep or placebo) and have an assessment after the 8th dose (with other subjects excluded from this supplemental analysis). Informal comparisons of the resulting analyses (p-values, point estimates and treatment differences) will be used to assess whether the three subsets of subjects, with different PK characteristics, have similar responses.

All subjects who were randomized to receive Q2W and who received correct treatment at each administration until week 12 (or until discontinuation of study drug, whichever came first) will be summarized with week 12. The number and proportion of subjects achieving ACR50, as an additional supplemental analysis to understand the impact of dosing errors.

An analogous analysis of subjects who were randomized to receive izokibep Q4W will also be reported. This will classify such subjects into two subsets:

- Received no more than four consecutive doses of placebo
- Received more than four consecutive doses of placebo.

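### SAP 6.6.2: the 8-dose rule in the Q2W dosing-error supplement applies to the Q2W subsets but not to placebo, which probably shifts their differences slightly towards izokibep (low priority)

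*SAP*

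**What the plan says.** SAP 2.1 reports that the Q2W and Q4W arms were given the right amount of drug but possibly in the wrong order. SAP 6.6.2 (Q2W and Q4W Supplemental Analyses) responds by sorting Q2W subjects on their longest run of like doses in the first 16 weeks. The four categories are reduced to three subsets, and the primary analysis is run in each, "comparing each subset of subjects to the entire group of placebo subjects".

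The next sentence classifies subjects by the doses they actually took. They are "included only if the subjects receive at least 8 total doses (izokibep or placebo) and have an assessment" later than the eighth dose; all others leave this analysis. No matching condition is stated for placebo.

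On the use of the results, the SAP says: "Informal comparisons of the resulting analyses (p-values, point estimates and treatment differences) will be used to assess whether the three subsets of subjects" respond alike.

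The analysis being re-run is the one in SAP 6.6.1, where "Subjects with missing ACR50 assessments at Week 16 will be imputed as non-responders". Such subjects stay in the denominator.

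**The concern.** The two sides of each contrast are selected differently. A Q2W subject lost after, say, five doses and never seen at Week 16 is deleted. A placebo subject with the same history is kept and scored as a failure. If early losses respond less often than average, removing them raises the Q2W rate while the placebo rate keeps its early failures.

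This supplement is one of the SAP's main tools for judging what the dosing error did. Its p-values and treatment differences are all subset-versus-placebo quantities, so a reader could take one as a like-for-like estimate of Q2W efficacy under a given dosing pattern. The SAP does not commit to reporting how many Q2W subjects the rule removes, so that reader could not judge the effect of the selection.

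**Working it through.** **Plan's own figure.** The documents give no figure for this supplement. The response rates used here come from SAP 2.3: 20% placebo, 45% izokibep, 100 per arm, stated power 97%. With a pooled-variance normal approximation, SE under the null is √(2 × 0.325 × 0.675/100) = 0.0662 and SE under the alternative is √(0.20 × 0.80/100 + 0.45 × 0.55/100) = 0.0638. Power = Φ[(0.25 − 1.96 × 0.0662)/0.0638] = 97.0%, which agrees.

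**Who is excluded.** With weekly dosing from Week 0, dose 8 falls at Week 7. SAP 5.1.4 names its efficacy timepoints as "a timeframe that corresponds to a scheduled efficacy assessment (week 2, 4, 12, 16, 20, 24, 32, 36, 40 or 52", with no Week 8 among them. But the rule asks only for an assessment, not an efficacy assessment. The schedule of activities (Protocol 1.3) has a Week 8 visit, SAP 6.7.3 lists Week 8 laboratory tests, and subjects who stop drug should have an end-of-treatment visit within 14 days. A subject with 8 doses will usually meet the second condition, so those excluded are mainly subjects with fewer than 8 doses. Subjects lost after meeting the rule stay in as failures in both arms.

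**Size of the shift.** Let
- p0 = 20%, the placebo rate under non-responder imputation (SAP 2.3);
- d = the share of placebo subjects the same rule would exclude (assumed; not in the documents);
- q = their Week 16 response rate under non-responder imputation (assumed).

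Filtered placebo rate = (p0 − d·q)/(1 − d). The planned contrast exceeds the same-rule contrast by (filtered rate − p0) = d(p0 − q)/(1 − d).

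| | d = 2% | d = 5% | d = 10% |
|---|---|---|---|
| q = 0 | 0.4 | 1.1 | 2.2 |
| q = 10% | 0.2 | 0.5 | 1.1 |
| q = 20% | 0 | 0 | 0 |
| q = 30% | −0.2 | −0.5 | −1.1 |

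(percentage points; for example 0.10 × 0.20/0.90 = 2.2)

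**Example at the planned rates**, d = 10% in both arms, q = 0. Filtered Q2W rate = 45/0.9 = 50.0%; filtered placebo rate = 20/0.9 = 22.2%. Planned contrast: 50.0 − 20.0 = 30.0 points. Same-rule contrast: 50.0 − 22.2 = 27.8. All randomized: 25.0.

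**Against sampling error.** A simulation used 200,000 trials per d, 20% response in both arms, q = 0, and 33 Q2W subjects (assumed one third of 100) versus 100 placebo. It had four strata (assumed 25% prior TNFi, 60% LEI > 0) and a Mantel-Haenszel difference with Sato variance. The shift was 0.05, 0.13 and 0.26 standard errors for d = 2, 5 and 10%. For d = 0, 2, 5 and 10%, rejections favouring izokibep were 1.8, 2.0, 2.4 and 3.3%, and those favouring placebo 4.6, 4.2, 3.7 and 2.9%. The two-sided total was 6.4, 6.2, 6.1 and 6.3%, so rejections move between tails without the total rising. The excess over 5% is already present at d = 0.

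**The case against.** **The stated purpose is unaffected.** The SAP wants to know whether the three Q2W subsets respond alike. All three are set against the same placebo group, so the placebo side cancels, exactly if unstratified and nearly so with Cochran-Mantel-Haenszel weights. This stands, and it is why the point is low priority.

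**The rule may have a purpose that does not concern placebo.** SAP 2.1 explains that "Subjects were assigned study drug in groups of four visits at a time"; eight doses cover two such groups, and Q2W subjects need enough doses to be sorted by run length. Placebo subjects need no sorting. That is plausible, though the SAP does not say it. It would explain filtering Q2W but not the unfiltered comparator.

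**The rule might cover placebo already.** The sentence names no arm and mentions both kinds of dose. But Q2W subjects receive both kinds, and the comparator is described as the whole placebo group. If both arms were meant, the text still needs the clarification.

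**A same-rule comparator is not like-for-like either.** This stands. In the example it removes 2.2 of the 5.0 points of excess over 25. The other 2.8 come from conditioning on continued treatment, and the randomized placebo arm becomes a second post-randomization subset. Hence both comparators should be shown.

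**The direction is not assured.** Protocol 7.1 encourages subjects who stop drug to remain for efficacy assessment, and observed Week 16 data are used whatever the treatment status. Some excluded subjects may therefore be observed responders, making q positive.

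**Conclusion.** The asymmetry is real on the natural reading of SAP 6.6.2, and its consequence is small. The subset-versus-placebo differences are likely to lean towards izokibep by 0.4 to 2.2 points for d between 2 and 10% with q = 0, less if some excluded subjects respond, and the other way if they respond above 20%. The values of d and q, the subset size of 33 and the stratum mix are assumptions.

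A reader might go further and infer any of three things that the documents do not support:
- That the Q2W efficacy claim is biased. The alpha-controlled Q2W test uses all randomized subjects (SAP 4.2 and 6.6), and this supplement lies outside the testing sequence.
- That the comparison among the three Q2W subsets is invalid. The asymmetry essentially cancels there.
- That false positives are inflated. Under the simulated conditions the two-sided rejection rate did not rise, and the SAP calls the comparisons informal.

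What remains is a cheap improvement to a supplemental table that might otherwise be read as like-for-like.

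**What to change.** Add to SAP 6.6.2:

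> *The same inclusion rule (at least 8 total doses received and an assessment after the 8th dose) will be applied to the placebo comparator; results against all randomized placebo subjects will be shown alongside; the number excluded by the rule will be reported by arm.*

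The wording should count doses, not injections: Protocol 6.1.1 gives two injections per administration, so a threshold of 8 injections would hold placebo to only 4 doses. The rule can be computed for placebo because "The total number of doses expected to be administered during Period 1 is therefore 16 for all groups" (SAP 6.5). Use the same sentence in the Q4W analogue if the rule is used there. Keep the classification by doses actually received. Showing the excluded Q2W subjects as their own row (number, and Week 16 ACR50 under non-responder imputation) would make the effect of the filter visible.

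The cost is one sentence, one column and one row. The filtered placebo group is slightly smaller: in the simulation the standard error rose by about 0.04, 0.10 and 0.20 points for d = 2, 5 and 10% (8.7 to 8.9 at 10%). No primary or secondary analysis changes.

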9.1.1. Multiplicity Adjustment and Type I Error Rate

Hypotheses tested will be adjusted to control the familywise error rate in the strong sense at $\alpha = 0.05$, 2-sided.

The statistical comparisons for the primary efficacy endpoint and the secondary endpoints, all at Week 16, will be carried out in sequential order. The primary endpoint, comparing izokibep dosed QW to placebo, will be tested first, with significance concluded if $p < 0.05$.

Testing of secondary endpoints, comparing izokibep dosed QW to placebo, will only be carried out if all prior tests, including the tests of the primary endpoint, first show significance with $p < 0.05$. If all primary and secondary endpoints, comparing izokibep doses QW to placebo, are

significant, testing of izokibep doses Q2W to placebo will begin and follow the same order. As long as all prior tests are significant, testing will proceed in the following order:

- The primary endpoint, achieving ACR50 at Week 16, comparing izokibep dosed QW to placebo.
- The first secondary endpoint, achieve PASI90 at Week 16 in subjects with $\geq 3\%$ BSA psoriasis at baseline, comparing izokibep dosed QW to placebo.
- The second secondary endpoint, achieving resolution of enthesitis at Week 16 in subjects that had enthesitis (LEI > 0) at baseline, comparing izokibep dosed QW to placebo.
- The third secondary endpoint, achieving MDA at Week 16, comparing izokibep dosed QW to placebo.
- The fourth secondary endpoint, achieving ACR20 at Week 16, comparing izokibep dosed QW to placebo.
- The fifth secondary endpoint, achieving improvement in PsAID of at least 3 units at Week 16 compared to baseline in subjects with PsAID ≥ 3 at baseline, comparing izokibep dosed QW to placebo.
- The sixth secondary endpoint, change in physical function of HAQ-DI from baseline to Week 16, comparing izokibep dosed QW to placebo.
- The primary endpoint, achieving ACR50 at Week 16, comparing izokibep dosed Q2W to placebo.
- The first secondary endpoint, achieve PASI90 at Week 16 in subjects with $\geq 3\%$ BSA psoriasis at baseline, comparing izokibep dosed Q2W to placebo.
- The second secondary endpoint, achieving resolution of enthesitis at Week 16 in subjects that had enthesitis (LEI > 0) at baseline, comparing izokibep dosed Q2W to placebo.
- The third secondary endpoint, achieving MDA at Week 16, comparing izokibep dosed Q2W to placebo.
- The fourth secondary endpoint, achieving ACR20 at Week 16, comparing izokibep dosed Q2W to placebo.

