## 2. Protocol Details

### 2.1. Overall Study Design

This is a multicenter, randomized, double-blind, placebo-controlled, Phase 2b/3 Study to evaluate the clinical question of the effects of the efficacy and safety of izokibep in subjects with active psoriatic arthritis (PsA) who are tumor necrosis factor-alpha inhibitor (TNFi) naïve, who have had an inadequate response or intolerance to TNFi, or for whom TNFi is contraindicated. Approximately 325 subjects with active PsA will be enrolled. The study consists of up to a 28-day (4-week) screening period, a 51-week treatment period, and a follow-up period with visits at 8 weeks and 14 weeks after the last dose of study drug to assess safety and immunogenicity.

Subjects meeting eligibility criteria will be randomized into 1 of 4 treatment groups in a 4:4:4:1 ratio as follows:

- Group 1 (n=100): placebo every week (QW) from Day 1/Week 0 to Week 15, then izokibep 160 mg QW from Week 16 to Week 51.
- Group 2 (n=100): izokibep 160 mg QW from Day 1/Week 0 to Week 51.
- Group 3 (n=100): izokibep 160 mg every 2 weeks (Q2W) from Day 1/Week 0 to Week 50, with matching placebo Q2W until Week 51 for the weeks in between izokibep doses to maintain the blind.
- Group 4 (n=25): izokibep 80 mg every 4 weeks (Q4W) from Day 1/Week 0 to Week 48, with matching placebo QW until Week 51 for the weeks in between izokibep doses to maintain the blind.

Randomization will be stratified by prior TNFi use (Yes/No) and enthesitis (Leeds Enthesitis Index [LEI] > 0/LEI = 0). Anticipated enrollment of subjects previously treated with TNFi is 20% to 30%. The number of subjects without enthesitis entering into the study (LEI = 0 at baseline) will be capped at 70%.

Subjects will complete study assessments according to the study visits outlined in the Schedule of Activities (SoA) in the protocol. The primary endpoint will be assessed at Week 16. The last dose of study drug will be administered on Week 51.

Starting at Week 24, subjects who do not meet clinical Disease Activity for PsA (cDAPSA) low disease activity (cDAPSA  $\leq$ 14) at 2 consecutive visits (e.g. at Week 20 and Week 24) will be discontinued from study drug and can receive standard of care as deemed appropriate by the investigator.

An End of Treatment (EOT) visit will be conducted at Week 52. A Safety Follow-up visit will be conducted at Week 59. A pharmacokinetic/anti-drug antibody (PK/ADA) Follow-up and

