### 2.3. Sample Size and Power

Response rates for ACR50 are expected to be 20% for placebo and 45% for a dose regimen of 160 mg izokibep (QW or Q2W or both). With 100 subjects receiving placebo and 100 subjects receiving a dose regimen of 160 mg izokibep, there will be 97% power to show a difference in the primary endpoint of ACR50 response rate. If a 45% response rate is observed with a dose regimen of izokibep, the 2-sided 95% confidence interval for the true response rate will have a half-width of approximately 10 percentage points.

Up to 60% of subjects are expected to have enthesitis at baseline, based on the LEI. Response rates, proportion of subjects who have LEI = 0 at Week 16, are expected to be 25% for placebo and 60% for subjects receiving izokibep. With 50 subjects with enthesitis at baseline receiving placebo and 50 subjects receiving a dose regimen of izokibep, there will be 95% power to show a difference in the secondary endpoint of resolution of enthesitis. A lower rate of enthesitis at baseline will result in a lower power, but power will be at least 80% with the same assumptions on response rate, if 30 subjects with enthesitis at baseline receive placebo and 30 subjects receive a dose regimen of izokibep.

With 25 subjects receiving izokibep 80 mg Q4W, the 2-sided 95% confidence interval for the true response rate will have a half-width of up to approximately 20 percentage points.

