The null hypothesis of equal response rates will compare each dosing regimen of izokibep to the placebo group. A stratified test of response rates will be used. Within each of the strata used for randomization, the response rate for each treatment group and corresponding standard error will be calculated. If a subject is incorrectly classified into a stratum during the randomization process, the analysis will use the correct classification, not the classification used during randomization. The difference in response rates (risk difference) will be calculated for each stratum. The common risk difference among the strata and associated standard error will be estimated by combining the observed risk differences using Cochran-Mantel-Haenszel weighting. The estimated risk difference divided by the standard error will be used as the test statistic and a p-value calculated assuming that the test statistic follows a standard normal distribution under the null hypothesis. A confidence interval on the difference will be calculated using analogous methods. Analyses at earlier timepoints when data to calculate the ACR50 are collected will also be presented using the same methodology. P-values from earlier timepoints will be presented for descriptive purposes, not part of the alpha-preserving multiple testing strategy.

The number and proportion of subjects achieving ACR50 in each treatment group will be reported at each scheduled assessment, along with Clopper-Pearson 95% CI without strata. The common risk difference with Cochran-Mantel-Haenszel weighting will be used to calculate a 95% CI for difference in response rates. A bar graph showing the proportion of subjects achieving ACR50 for each treatment group along with the associated p-value will be produced. ACR50 results will also be listed.

Sample SAS code with stratification factors of comparing each dosing regimen of izokibep to the combined placebo group is given as following:

```
ods output commonpdif = ;
proc freq data= ;
  tables stratum * treatment * response / cmh commonriskdiff (test=mh cl=mh);
  weight count / zeros;
run;
```

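### P-values against placebo cannot show whether the three Q2W dosing-sequence subsets respond alike; SAP 6.6.2 plans no interval for the difference between subsets

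*SAP*

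**What the plan says.** SAP 2.1 reports that, before database lock, subjects randomized to Q2W or Q4W were found to have received the right amount of drug over each four-week block but possibly in the wrong order. The Q2W and Q4W paragraph of SAP 6.6.2 responds with a supplementary analysis. Q2W subjects are grouped by the longest run of consecutive izokibep or placebo doses in Period 1. The two least disturbed of four groups are merged, which leaves three subsets. The primary analysis is run in each, "comparing each subset of subjects to the entire group of placebo subjects". The results are then compared informally: "p-values, point estimates and treatment differences) will be used to assess whether the three subsets of subjects, with different PK characteristics, have similar responses".

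No direct contrast between subsets is specified there or elsewhere. The pairwise p-values in SAP 6.6.5 are between the four treatment arms. SAP 6.6.6, which also asks whether response is consistent across subgroup levels, reports no p-values for its subgroups.

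**The concern.** The question is whether the Q2W subsets differ from each other. Each planned test has a different null hypothesis, namely that the subset's ACR50 rate equals placebo's. Two subsets with the same response can give very different p-values if one is small, and two subsets with different responses can both be clearly significant. A reader who gives weight to the p-values could therefore see an effect of mis-sequencing where there is none, or miss one that exists.

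At stake is the interpretation of the Q2W result. Q2W is part of the primary objective and comes second in the testing sequence. The primary test itself does not depend on this comparison.

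**Working it through.** **Inputs from the documents.** Two-sided tests ("All alternative hypotheses will be two-sided", SAP 6.1) at 0.05. Rates from SAP 2.3: "Response rates for ACR50 are expected to be 20% for placebo and 45% for a dose regimen of 160 mg izokibep". Planned arm sizes are 100 placebo and 100 Q2W (SAP 2.1). The statistic is from SAP 6.6.1: "The estimated risk difference divided by the standard error will be used as the test statistic".

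**Assumed.** The subset sizes, varied over a range. Hand calculations are unstratified and use expected rates, some of which are not whole counts (45% of 10, for example).

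**Reproducing the plan's figure.** SAP 2.3 states: "With 100 subjects receiving placebo and 100 subjects receiving a dose regimen of 160 mg izokibep, there will be 97% power". With pooled rate 0.325, the null SE is √(2 × 0.325 × 0.675/100) = 0.0662. The SE under the alternative is √((0.16 + 0.2475)/100) = 0.0638. Power = Φ((0.25 − 1.96 × 0.0662)/0.0638) = 97.0%, which agrees.

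**Same response, different p-values.** For a subset of size n at 45% against 100 placebo subjects at 20%, z = 0.25/√(0.16/100 + 0.2475/n), and power is approximately Φ(z − 1.96).

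| n | z | p at the expected rates | Power vs placebo |
|---|---|---|---|
| 10 | 1.54 | 0.124 | 34% |
| 30 | 2.52 | 0.012 | 71% |
| 50 | 3.09 | 0.002 | 87% |

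A pooled-variance formula gives 45% at n = 10 and 88% at n = 50. The unpooled form is used in the table because it is closer to the planned statistic.

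**How often the three results split.** These are simulated trials with all subsets truly at 45%, a shared placebo group of 100 at 20%, and a split defined as some subsets below 0.05 and some above. Stratified runs assume 25% prior TNFi use and 55% with enthesitis.

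| Assumed sizes | Method | Split |
|---|---|---|
| 33/33/34 | unstratified | 48% |
| 30/30/30 | stratified | 54% |
| 50/35/15 | unstratified | 62% |
| 15/35/40 | stratified | 64% |
| 60/30/10 | unstratified | 72% |
| 10/30/50 | stratified | 73% |
| 70/20/10 | unstratified | 77% |

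A hand check for 10/30/50 treats the tests as independent. All are significant with probability 0.34 × 0.71 × 0.87 = 0.21, and none with probability 0.66 × 0.29 × 0.13 = 0.02, so the split is about 77%. The shared placebo group brings this down to the simulated 73%.

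**Different response, both significant.** Take 40% in 60 subjects and 60% in 30. Against placebo, p = 0.008 and p = 0.00004. The direct difference is 20 points, 95% CI about −1 to 41, p = 0.07.

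**Precision of a direct contrast.** At 45% in both subsets, half-width = 1.96 × √(0.2475 × (1/n₁ + 1/n₂)):

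- 30 vs 30: 1.96 × √0.0165 = 25 points
- 10 vs 50: 1.96 × √0.0297 = 34 points
- Q4W, 12 vs 13 of the 25 planned: 1.96 × √0.0397 = 39 points

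**The case against.** The strongest reply is that the SAP does not define similarity as three p-values on the same side of 0.05. It plans an informal look at three things, and two of them are relevant. Because all subsets share one placebo group, placebo cancels when treatment differences are compared: (A − placebo) − (B − placebo) = A − B, apart from stratum weighting. This stands. The split percentages describe only what the p-values contribute, not the error rate of the planned judgement.

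A reader might infer that three significant results would hide a real difference. The documents do not support that, since the point estimates must also be examined. In simulated trials with true rates of 55/45/35% where all three subsets were significant, the observed rates still differed by a median of 17 to 24 points.

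A reader might also infer that no uncertainty is reported. SAP 6.6.1 gives a Clopper-Pearson interval for each group and a CI for each difference from placebo. Only the interval for a between-subset difference is missing.

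Nor is this the only check on the sequence error. The SAP places all Q2W tests after all QW tests, summarizes correctly dosed Q2W subjects at earlier visits including Week 12, and looks at ACR20 and PASI75 at Week 4, when sequencing was still correct.

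Finally, a direct contrast is weak. A 2-df test across subsets detects the 55/45/35% spread in only 21% to 26% of trials. That is a reason to report intervals rather than another test. It is not a reason to keep p-values that address a different null hypothesis.

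**Conclusion.** The point holds as a matter of interpretation. Versus-placebo p-values are named as evidence on a question they do not address, and the one quantity that addresses it directly, a between-subset difference with its interval, is not planned. At identical true response the p-values split on significance in roughly half to 70% of trials over most of the sizes tried, and in 77% at the most uneven. This rests on the SAP's 20% and 45% rates and on assumed subset sizes.

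Three stronger statements go too far. Unequal size is not the main cause of the splits, since equal subsets of 30 already split 54% of the time through low power and sampling noise. Splits are not the rule in every case, since 33/33/34 gives 48%. The primary Q2W test is not compromised, since this analysis is supplementary, informal and outside the alpha-controlled sequence. The change is a cheap improvement that should be made, not a defect in the confirmatory analysis.

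**What to change.** In SAP 6.6.2:

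- Remove the versus-placebo p-values from the similarity judgement, in line with SAP 6.6.6.
- Report differences in Week 16 ACR50 between the Q2W subsets with 95% CIs. Use the merged, least disturbed subset as reference, and adjust for prior TNFi use and enthesitis where numbers allow.
- State that wide intervals cannot establish similarity, so the absence of a visible difference is not evidence that mis-sequencing had no effect.
- Keep the subset-versus-placebo estimates as description.
- Treat the two Q4W subsets the same way, descriptively only.

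The cost is one extra table and a few sentences, with no new data and no change to alpha or the testing order. The downside for the sponsor is that the imprecision becomes explicit.
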